6.5.1.9 Exceptions

In this protocol, symptoms and signs related to PD will not be considered as AEs or captured on the eCRF, however, unexpected worsening of PD should be reported as an AE. The following hospitalization scenarios will not be considered AEs:

- Hospitalization for a preexisting condition, provided that the following criteria are met:
 - The hospitalization was planned prior to the study or was scheduled during the study when elective surgery became necessary because of the expected normal progression of the disease or
 - The patient has not experienced an AE

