22. Alcohol and/or drug abuse within 6 months prior to Screening (Visit 1), as defined by Diagnostic and Statistical Manual – Fifth Edition Text Revision Criteria for Substance Abuse
23. Females who are pregnant or breastfeeding
24. Sexually active female patients, who are not surgically sterile or at least 2 years postmenopausal prior to Screening (Visit 1), and do not agree to utilize a highly effective hormonal method of contraception (an intrauterine device or vasectomized male partner is also acceptable), in combination with a barrier method, from Screening (Visit 1) through at least 4 weeks after the completion of study treatment
25. Male patients not using highly effective contraception or not agreeing to continue highly effective contraception through at least 90 days after the completion of study treatment
26. Known allergy to any ingredients of the study treatment or placebo (pridopidine, silicified microcrystalline cellulose, magnesium stearate)
27. Treatment with any investigational product within 30 days of Screening (Visit 1) or patients planning to participate in another clinical study assessing any investigational product during the study
28. Planned elective surgery during study participation

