6.5.1.2 Serious Adverse Events

An SAE is defined as any event that:

- results in death
- is immediately life-threatening
- requires inpatient hospitalization or prolongation of existing hospitalization
- results in persistent or significant disability/incapacity
- is a congenital anomaly/birth defect

Important medical events that may not result in death, be life-threatening, or require hospitalization may be considered SAEs when, based upon appropriate medical judgment, they may jeopardize the patient or may require medical or surgical intervention to prevent one of the outcomes listed in this definition. Examples of such medical events include allergic bronchospasm requiring intensive treatment in an emergency room or at home, blood dyscrasias or convulsions that do not result in inpatient hospitalization, or the development of drug dependency or drug abuse.

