6.6 Data Safety Monitoring Board

During the study, an independent Drug Safety Monitoring Board (DSMB) consisting of a neurologist, a cardiologist and a statistician will periodically review accumulating unblinded safety data. The DSMB will meet when first 30 patients have been enrolled and have completed 2 weeks of maintenance treatment on 150 mg BID, 100 mg BID dose or placebo (Visit 3) Thereafter the DSMB will determine the meeting frequency as they deem necessary. Additionally, DSMB will evaluate all SAEs in real-time.

If a significant safety concern emerges in the high dose treatment, the DSMB will have the authority to discontinue individual patients from the study, discontinue an arm and/or halt the study. In case the 150 mg BID arm is discontinued, all patients who are on maintenance treatment with 150 mg BID arm will immediately be discontinued from the study and will undergo a down-titration period. Patients, randomly assigned to the 150 mg BID arm but still in the titration period, will be switched to the 100 mg BID arm. Newly enrolled patients will be randomized to the 100 mg BID dose or placebo. Further details will be provided in the DSMB charter.

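### Protocol Section 6.5.1.9 asks for its hospitalisation criteria to be met but joins them with 'or', so either one literally takes an admission for a pre-existing condition out of AE and 24-hour SAE reporting

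*Protocol*

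**What the plan says.** Protocol Section 6.5.1.9 is headed Exceptions. It first removes signs and symptoms of Parkinson's disease (PD) from AE recording, while keeping unexpected worsening of PD as an AE. It then states: "The following hospitalization scenarios will not be considered AEs". One scenario follows: "Hospitalization for a preexisting condition, provided that the following criteria are met".

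Two sub-bullets give the criteria:

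- **A.** "The hospitalization was planned prior to the study or was scheduled during the study when elective surgery became necessary". This sub-bullet closes with the words "elective surgery became necessary because of the expected normal progression of the disease or".
- **B.** "The patient has not experienced an AE".

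Four other parts of the protocol bear on the same admission:

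- Section 6.5.1.2 makes an event serious if it "requires inpatient hospitalization or prolongation of existing hospitalization".
- Section 6.5.1.4 requires every AE to be recorded. It treats a condition present at screening that later deteriorates as an AE, and it asks for AEs arising from disease progression to be reported.
- Section 6.5.1.5 sends to 24-hour reporting those AEs that meet an SAE criterion.
- Section 6.5.1.3 has patients asked at every visit whether they have been hospitalised.

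The SAP has no rule on this exemption. Its Section 15.3 includes SAEs in the by-group overall AE summary.

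**The concern.** The lead-in and the connector disagree. Criteria that must be met, in the plural, point to both being required; the *or* makes either sufficient. The two readings classify the same admission differently.

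The classification matters because of the order in which the protocol applies its definitions. Seriousness is a property of an AE, and Section 6.5.1.5 acts only on AEs. An admission declared not to be an AE is therefore never tested against the seriousness criteria. Because the section is presented as a set of exceptions, a site could reasonably read it as overriding the general rules in Sections 6.5.1.2 and 6.5.1.4.

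At stake is the completeness of SAE capture: prompt reporting to the sponsor, the monitoring board's review (Section 6.6: "DSMB will evaluate all SAEs in real-time") and the SAE counts by treatment group. Sample size, power and type I error are not affected.

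**Working it through.** No figure in the plan depends on this rule, so there is nothing to reproduce. The check is a truth table, followed by a comparison with the other sections.

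**Step 1. The two readings.** A = planned before the study, or elective surgery scheduled during it for expected progression. B = no AE experienced. All rows concern an admission for a pre-existing condition.

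| A | B | Exempt under A *or* B | Exempt under A *and* B |
|---|---|---|---|
| yes | yes | yes | yes |
| yes | no | yes | no |
| no | yes | yes | no |
| no | no | no | no |

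The wording as printed exempts 3 of 4 combinations; the reading implied by the lead-in exempts 1 of 4. The difference is 3 − 1 = 2 combinations: planned with an AE, and unplanned with no AE. These are logical cells, not proportions of admissions.

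**Step 2. Planned, with an AE.** What is exempted is the hospitalisation. The AE itself is still to be recorded under Section 6.5.1.4, and if it prolongs the stay it is serious under Section 6.5.1.2. The possible loss is the seriousness: a site that treats the whole admission as exempt may record the AE without counting the prolonged stay.

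**Step 3. Unplanned, no AE.** If the admission reflects deterioration of the pre-existing condition, Section 6.5.1.4 makes that deterioration an AE, so B is false and the exemption fails. The cell stays open only where the investigator concludes that no AE occurred. Two other rules lean that way: the opening sentence of Section 6.5.1.9 on PD signs and symptoms, and the close of Section 6.8, which keeps disease-associated findings out of AE reporting unless judged more severe than expected.

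**Step 4. Would *and* alone be enough?** Not quite. B has no time limit and no link to the admission. Under a bare *and*, an unrelated mild AE months earlier makes B false and removes the exemption from a genuinely pre-planned admission. B has to be tied to the admission.

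**Step 5. Weight of one event in the tables.** SAP Section 9.3 says that the study stopped before 30 subjects were enrolled, so at most 29. If they split evenly over three arms (an assumption; the documents give no arm counts), that is at most 29/3 ≈ 9.7 per arm, and one subject carries at least 1/9.7 ≈ 10 percentage points of an arm's SAE percentage. This shows how sensitive the table is to one case. It does not estimate how many cases are missed.

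**The case against.** The best reply is that the rest of the protocol closes most of the gap. An unplanned admission for a pre-existing condition will usually reflect deterioration, which Section 6.5.1.4 calls an AE. Section 6.5.1.9 itself keeps unexpected worsening of PD as an AE. B speaks of an AE experienced, not one declared, so failing to recognise an AE is non-compliance that no connector cures. An AE during a planned admission remains recordable. All of this stands, and it limits the effect for a careful investigator. It does not remove the contradiction, because a site may take the exceptions section as overriding the general one.

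Three stronger readings are tempting and are not supported:

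- *That emergency admissions for confusion or a fall put down to PD escape through the* or. Any such exclusion would come from the section's opening sentence on PD signs and symptoms, which *and* would leave in place. That same sentence keeps unexpected worsening reportable.
- *That SAE review was the monitoring board's only input before its first meeting.* Section 11.1.1 adds AEs to the real-time review.
- *That the planned branch is nearly empty, so the unplanned one dominates.* The exclusion of "Planned elective surgery during study participation" does not reach surgery that becomes necessary later, or planned admissions without surgery.

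**Conclusion.** The point holds as an internal contradiction in an operative safety-reporting rule. Read literally, either criterion takes an admission for a pre-existing condition out of AE reporting and, through Section 6.5.1.5, out of 24-hour SAE reporting. As a result, an unplanned admission, or the seriousness of an AE during a planned one, may go uncounted.

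The size in terms of events is unknown, since the documents give no admission rate. The conclusion assumes that some sites follow the literal wording or let the exceptions section take precedence. Where investigators apply Section 6.5.1.4 and the unexpected-worsening clause, little or nothing is lost. It would go too far to say that SAEs necessarily escape reporting. The supportable statement is that the protocol gives two answers for the same admission, and that SAE capture should not depend on which one a site reads.

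**What to change.** In Protocol Section 6.5.1.9:

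1. Replace the *or* between the two sub-bullets with *and*, and state in the lead-in that both criteria must be met.
2. Reword the second criterion along these lines: no AE led to, occurred during or prolonged the hospitalisation.
3. Add that the deterioration rule in Section 6.5.1.4 and the seriousness criteria in Section 6.5.1.2 continue to apply, so that Sections 6.5.1.2, 6.5.1.4, 6.5.1.5 and 6.5.1.9 agree.

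The cost is a short amendment, a memo to sites and possibly a few more SAE reports. No dose, endpoint, sample size or analysis changes. SAP Section 2 describes the study as ongoing and the database as not yet locked. While that remains so, hospitalisations elicited at visits but classed as non-AEs can be queried and, where needed, reclassified before lock.

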6.5.1.10 Follow-Up of Patients Reporting Adverse Events

All AEs must be reported in detail on the appropriate page in the eCRF and followed to satisfactory resolution, until the investigator deems the event to be chronic or not clinically significant, or until the patient is considered to be stable.

6.5.2 ECG: QTc Parameters

At Baseline (Visit 2) and at every visit thereafter, triplicate 12-lead ECG evaluations will be assessed before, and 1 to 2 hours after the study treatment dose administered at the clinic (approximate C_{max}). A triplicate 12-lead ECG measure is comprised of three 10-second ECG recordings. The time interval between each of the three individual ECG recordings should be approximately 60 seconds. When concomitant with ECG recording, PK samples will be collected within 30 minutes after the ECG recording.

At Screening (Visit 1), a single resting 12-lead ECG will be conducted after at least 5 minutes of supine rest. If there is evidence of a prolonged QTcF interval (defined as a QTcF interval of >450 msec), then the ECG will be repeated twice within 10 minutes of the first ECG recording. The time interval between the two additional ECGs should be approximately 60 seconds. The mean of the three screening measurements will be used to determine whether or not the patient is suitable for inclusion in the study. The decision to repeat an ECG will be made by the investigator and/or the physician assessing the ECG.

At Baseline (Visit 2) and at every clinic visit thereafter, a triplicate 12-lead ECG evaluation (three 10-second recordings) will be conducted before and 1-2 hours after study treatment dose administration. When applicable, PK samples will be collected within 30 minutes after the ECG recording. The QTcF values will be determined by the average of the 12-lead ECG triplicate.

The patient must be in a supine position and resting for at least 5 minutes prior to each ECG measurement. Where applicable, ECG measurements should be taken prior to vital sign measurements and blood being drawn for clinical laboratory or PK evaluations. A qualified physician at the central ECG vendor will be responsible for interpreting the ECG and send results within 24 hours. However, every ECG should be reviewed immediately at site for the purpose of determining any gross abnormality (like new atrial fibrillation or QTcF prolongation) that might affect patient safety and not allow dosing. If the local ECG reading results at the site match any of the discontinuation criteria (see [Section 4.2.1](#)), the patient should stop taking study treatment until the central ECG reader's report is received. If the central reader does not report a QTcF interval that would lead to discontinuation according to the above, then the patient should restart study treatment. Any ECG finding that is judged by the investigator or the physician from the central ECG vendor as a clinically significant change (worsening) compared with a Visit 2 value will be considered an AE, recorded on the source documentation and transcribed onto the eCRF and monitored as described in [Section 6.5.1.4](#).

6.5.4 Physical and Neurological Examination

The physical and neurological examination of all major body parts (excluding a genitourinary exam) will be carried out by an Investigator (who is a neurologist by medical training) at the time points noted in the schedule of assessments ([Table 4](#)). Any clinically significant changes during the treatment period will be recorded on the eCRF.

6.5.5 Concomitant Medications

The concomitant medication assessments will be carried out at the time points noted in the schedule of assessments ([Table 4](#)).

6.5.6 Assessment of Suicidal Ideation and Behavior (C-SSRS)

Suicidal ideation and behavior will be assessed using the "Screening" part of the C-SSRS. Each part of the C-SSRS consists of three question groups (suicidal ideation, intensity of ideation, suicidal behavior). It is intended for use by individuals who have been trained in its administration. Ultimately the presence of suicidality depends on clinical judgment.

Throughout the clinical study patients will be monitored for suicidality potential using the C-SSRS scale. Patients who have a C-SSRS suicidal ideation score > 2 will be sent for further evaluation by a mental health care specialist who will assess for imminent risk. The score alone

will not serve as a reason for immediate treatment discontinuation. The assessments will be carried out at the time points noted in the schedule of assessments ([Table 4](#)).

6.5.7 Questionnaire for Impulsive-Compulsive Disorders in Parkinson's Disease-Rating Scale (QUIP-RS)

QUIP-RS is a rating scale designed to measure severity of impulsive-compulsive disorders (ICD) symptoms and support a diagnosis of ICD and related disorders in PD. Four subscales for ICDs (gambling, sexual compulsions, compulsive buying and compulsive eating) have possible scores between 0 and 16 and suggested cut-offs (scores validated as indicative of ICDs via clinical interview) as follows: gambling (≥ 6); compulsive buying (≥ 8); sexual compulsions (≥ 8); compulsive eating (≥ 7); and combined ICDs (≥ 10). The QUIP-RS also includes measures for hobbyism (involvement in organized activities like writing or computer use) and punding (repeating activities like cleaning). The assessments will be carried out at the time points noted in the schedule of assessments ([Table 4](#)).

6.5.8 Other Assessments

An eligibility review of screened patients to help protect the safety of patients and confirm eligibility will be performed by independent neurologists serving on the EAC (Clintrex) to determine if a patient is correctly diagnosed and to ensure that patient meets the criteria for enrollment in order to avoid unnecessary risks for the patients. Potential patients will be reviewed at least 24 hours before a potential randomization to ensure they meet the criteria for enrollment.

6.6 Data Safety Monitoring Board

During the study, an independent Drug Safety Monitoring Board (DSMB) consisting of a neurologist, a cardiologist and a statistician will periodically review accumulating unblinded safety data. The DSMB will meet when first 30 patients have been enrolled and have completed 2 weeks of maintenance treatment on 150 mg BID, 100 mg BID dose or placebo (Visit 3) Thereafter the DSMB will determine the meeting frequency as they deem necessary. Additionally, DSMB will evaluate all SAEs in real-time.

If a significant safety concern emerges in the high dose treatment, the DSMB will have the authority to discontinue individual patients from the study, discontinue an arm and/or halt the study. In case the 150 mg BID arm is discontinued, all patients who are on maintenance treatment with 150 mg BID arm will immediately be discontinued from the study and will undergo a down-titration period. Patients, randomly assigned to the 150 mg BID arm but still in the titration period, will be switched to the 100 mg BID arm. Newly enrolled patients will be randomized to the 100 mg BID dose or placebo. Further details will be provided in the DSMB charter.

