4.2 Withdrawal of Patients from Study Treatment and/or the Study

The duration of the study is defined for each patient as the date signed written informed consent is provided through the last safety follow-up visit at Visit 8. If a patient discontinues treatment, they will be encouraged to remain in the study and continue study visits and procedures for the full course of the study without receiving study treatment. Patients who withdraw from the

study before the Visit 7/ET visit and are not willing to continue study visits and procedures for the full course of the study will be asked, to undergo an ET visit that will include all evaluations that were intended to be performed at the final visit.

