6.5.1.3 Eliciting and Documenting Adverse Events

Adverse events will be assessed beginning at enrollment (date of signed informed consent) and up to visit of the safety follow-up period (Visit 8).

Serious AEs that occur more than 30 days after the reporting period need not be reported unless the investigator considers them related to study treatment.

At every study visit, patients will be asked a standard nonleading question to elicit any medically related changes in their well-being. Patients will also be asked if they have been hospitalized, had any accidents, used any new medications, or changed concomitant medication regimens (both prescription and OTC medications).

In addition to patient observations, any abnormal laboratory test results (haematology, clinical chemistry, or urinalysis) or other safety assessments (e.g., ECGs, radiological scans, vital sign measurements), including those that worsen from Visit 2, felt to be clinically significant in the medical and scientific judgment of the investigator are to be recorded as AEs or SAEs. In addition, AEs identified from review of other documents (e.g., patient diaries) that are relevant to patient safety will be documented on the AE page in the eCRF.

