7.9.1 Analysis of Primary Endpoint

The primary endpoint will be analyzed using a Mixed Model for Repeated Measures (MMRM) with no imputation using the mITT population. The Baseline (Visit 2) score will be included as a covariate and the treatment group (pridopidine 100 mg BID, pridopidine 150 mg BID or placebo), Visit 4, Visit 5, Visit 6 or Visit 7/ET, and the interaction between treatment group and visit as fixed factors in the MMRM. An unstructured covariance structure will be applied for MMRM. In case the model will not converge with the unstructured covariance structure, the heterogeneous Toeplitz structure (TOEPH) will be used instead. In case the model will not converge with the heterogeneous Toeplitz structure, heterogeneous compound symmetry will be used. The denominator degrees of freedom will be computed using the Kenward-Roger method. The difference between each dosage of pridopidine vs placebo at Visit 7/ET along with the 95% CIs and associated p-value will be estimated from the MMRM. The differences at Visit 4 and Visit 6 will be estimated as well from the same model.

Sensitivity analyses of the primary endpoint will be conducted in the ITT set with multiple imputation methods, both assuming that data are missing at random and not missing at random. The analysis assuming that data are not missing at random will be conducted with the Copy-Reference approach, i.e., assuming that the patients who have missing data will follow the trajectories of the placebo-treated patients after the first visit with missing data. Further sensitivity analysis will be conducted in the completer set with MMRM. In addition, sensitivity analyses will be conducted by including the retrieved drop-out data (data captured from the drop-outs after the end-of-study visit when the patient is free of study treatment) to the mITT analysis. All efforts will be made to perform scheduled efficacy assessments after patients discontinue.

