7.9.4 Safety Analyses

The safety analysis will be conducted on the safety set. The AEs will be coded according to the MedDRA and treatment-emergent adverse events (TEAEs) summarized by treatment group, system organ class and preferred term. Further summaries will be done by seriousness, severity, relationship to study treatment and actual dose at the time of onset.

Vital signs, ECG data and laboratory tests at baseline (last non-missing results prior to the first dose of study drug, each postbaseline visit, and changes from baseline to each of the postbaseline visits will be summarized with descriptive statistics. Shift tables for the laboratory tests based on a classification of values as low, normal, or high with respect to the reference range will be summarized.

For vital signs, orthostatic hypotension is defined as a reduction of 20 mmHg or more in systolic blood pressure, or a reduction of 10 mmHg or more in diastolic blood pressure, for the standing measurement compared to the supine measurement. The proportion of patients with orthostatic hypotension will be summarized with shift tables.

Prilenia Therapeutics

Protocol: PL101-LID201 Protocol Amendment 1/v2.0

Pridopidine

19 Nov 2019

For ECG data, absolute QTcF of >450 msec, >480 msec, and >500 msec, changes from baseline in QTcF>30 msec and <60 msec, and changes in QTcF>60 msec throughout the study will be summarized.

All other safety data will be summarized with descriptive methods.

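### On closure of the 150 mg BID arm, Protocol 6.6 takes its maintenance patients out of the study while Section 4.2 encourages discontinuers to stay, so their scheduled observation would end earlier than in the other arms

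*Protocol*

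**What the plan says.** Protocol Section 6.6 lets the DSMB close an arm if a significant safety concern emerges at the high dose. In that event "all patients who are on maintenance treatment with 150 mg BID arm will immediately be discontinued from the study", with down-titration to follow. Patients randomized to 150 mg BID but "still in the titration period, will be switched to the 100 mg BID arm", so they stay in the study. New patients go to 100 mg BID or placebo, and no text removes patients already in those two arms. Further detail is left to the DSMB charter, which is not among the documents.

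Section 4.2 gives the general rule: "If a patient discontinues treatment, they will be encouraged to remain in the study and continue study visits and procedures". Those unwilling to continue are asked for an ET visit with all the final-visit evaluations. The same distinction appears elsewhere:

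- Section 4.2.1 speaks of stopping the treatment or the study as alternatives. Its creatinine clearance rule stops treatment only.
- Section 5.8.1 ends dosing for an unblinded patient but encourages that patient to continue to the final visit.

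On data collection, Section 6.5.1.3 runs adverse events from consent "up to visit of the safety follow-up period (Visit 8"). Section 3.1.3 places the safety follow-up visit two weeks after Visit 7 or ET. Section 7.9.1 states: "All efforts will be made to perform scheduled efficacy assessments after patients discontinue". Section 7.9.4 has "treatment-emergent adverse events (TEAEs) summarized by treatment group", and SAP Section 15.3 lists numbers and percentages of subjects and event counts.

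**The concern.** The protocol gives two answers to one question: does a patient whose dosing is stopped leave the treatment or the study? The general answer favours staying. The specific answer for arm closure is to leave, and it applies only to the arm under suspicion.

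Two things would be at stake if closure occurred and sites followed Section 6.6 literally.

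- **Harm comparison.** Patients in 150 mg maintenance at closure would be observed for fewer scheduled days than patients in the arms they are compared with. The adverse event summaries in SAP Section 15.3 use no person-time denominator, so a shorter window would tend to lower the 150 mg percentages and counts.
- **Efficacy after discontinuation.** Section 7.9.1 plans a sensitivity analysis that adds retrieved drop-out data. Patients removed at closure would have no scheduled efficacy visits after ET to supply such data.

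**Working it through.** The plan states no figure for this situation, so the check starts from its calendar.

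**Inputs**

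- Maintenance: Days 29 to 112 (Protocol 5.2).
- Visit 7 on Day 112 and Visit 8 on Day 126, each ±1 day (Protocol Table 4). These agree with each other: 16 weeks × 7 = 112, and 112 + 14 = 126.
- Safety follow-up visit: 14 days after Visit 7 or ET (Protocol 3.1.3).
- Assumption A: the ET visit takes place on the closure day, t.
- Assumption B: t is uniform over the affected patient's Days 29 to 112.

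**Days lost for a given closure day**

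Last scheduled contact = t + 14. Days lost against Day 126 = 126 − (t + 14) = 112 − t.

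| Patient's day at closure | Last contact | Days lost | Share of 126 |
|---|---|---|---|
| 29 | 43 | 83 | 65.9% |
| 43 | 57 | 69 | 54.8% |
| 70 | 84 | 42 | 33.3% |
| 91 | 105 | 21 | 16.7% |
| 111 | 125 | 1 | 0.8% |

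Day 43 is two weeks into maintenance, the milestone that Section 6.6 sets for the first DSMB review.

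**Mean loss under assumption B**

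Mean t = (29 + 112)/2 = 70.5. Mean loss = 112 − 70.5 = 41.5 days, and 41.5/126 = 32.9%. Counting whole days 29 to 111 gives 42.0 days, or 33.3%.

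**Sensitivity to assumption A**

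Table 4, note c, allows a week for the ET visit. If every ET visit came 7 days after closure, the loss would be 105 − t, and zero from Day 105 on. The mean would be (76²/2)/83 = 34.8 days, or 27.6%.

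**What that could do to a crude percentage**

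Take a constant event rate over the whole window, on or off drug. A true 126-day incidence p is then seen as 1 − (1 − p)^(f/126) when contact ends on day f.

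| True p | f = 57 (closure on Day 43) | f = 84 (closure on Day 70) |
|---|---|---|
| 10% | 4.7% | 6.8% |
| 20% | 9.6% | 13.8% |
| 30% | 14.9% | 21.2% |
| 50% | 26.9% | 37.0% |

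These are upper bounds on the effect of leaving the study. Dosing stops at closure under either section, and stopping the drug may itself lower the event rate in the days not observed. They apply to affected patients, not to the whole arm.

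**The case against.** The strongest reply is that Section 6.6 does not leave these patients unobserved. A reader might infer from its wording that contact ends with the 4-day down-titration. That would put the mean loss at 126 − (70.5 + 4) = 51.5 days, or 41%. The documents do not support this. Section 4.2 and Table 4 provide for an ET visit, Section 3.1.2 ties down-titration to the end of maintenance or ET, and Section 3.1.3 adds a safety visit two weeks later. That is the same post-treatment interval that completers get after Visit 7. Sections 4.2.1 and 6.5.1.10 follow adverse events to resolution or stability, and Section 6.5.1.3 exempts serious events from reporting only beyond 30 days after the reporting period. The 41% figure therefore falls, as does any claim that recovery of known events would go unfollowed.

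Three further points stand in part:

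- **Not arm-wide.** Patients who have completed lose nothing, and those in titration switch and stay. The 33% is a mean per affected patient, not a loss for the arm.
- **Not drug exposure.** Most loss of on-drug time comes from closing the arm, which is not disputed. Section 7.9.4 also summarizes events by dose at onset, and SAP Section 15.1 tabulates duration of exposure. Neither supplies the missing off-drug observation or puts follow-up time into the crude percentages.
- **Retrieved data not ruled out.** Earlier 150 mg discontinuers could still contribute, so the sensitivity analysis would be thinner rather than impossible. The SAP, which takes precedence, lists only imputation under missing at random, so this consequence belongs to the protocol as written.

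It can also be said that Section 4.2 only encourages, that a specific rule may override a general one, and that the charter may settle the matter. Each is possible. None tells a site working from the protocol which visits apply after closure.

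**Conclusion.** The inconsistency is real and can be verified in the text. Sections 6.6 and 4.2 give different answers on whether patients stay in the study, and the Section 6.6 rule applies to one arm. Taken literally, patients in 150 mg maintenance at closure would lose on average about 41.5 of 126 days of scheduled observation (33%). This assumes a uniform closure day and ET on that day; it is about 28% if ET comes a week later. The range over single closure days runs from 66% at Day 29 to nearly nothing at Day 111. Almost all of this is off-treatment time, so the figure caps the under-counting of harm and does not estimate it.

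A reader might infer that the safety results of this trial are biased. They are not affected by this point. SAP Section 9.3 reports that the study ended before 30 subjects were enrolled and that no formal DSMB meeting was held, so the rule was not applied. What remains is a defect in the protocol text that matters if the text is reused.

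**What to change.** Reconcile Protocol Section 6.6 with Section 4.2, and align the DSMB charter, so that one consistent rule states:

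- whether patients in 150 mg maintenance at arm closure leave the treatment or the study;
- which scheduled safety and efficacy visits then apply to them;
- how adverse events are collected for them through Visit 8.

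No change is proposed to the decision to stop dosing, to the down-titration, or to the handling of patients still in titration.

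The cost is a short wording change in the protocol and the charter. If the reconciled rule keeps these patients in follow-up, they may have extra visits while off drug. The visits are already in Table 4, and Section 4.2 already encourages other patients who stop treatment to attend them. The sample size is unaffected.
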